9 DATA COLLECTION, SITE MONITORING, AND ADVERSE EXPERIENCE REPORTING

9.1 Data Management

Site personnel will collect, transcribe, correct, and transmit the data onto source documents, CRFs, and other forms used to report, track and record clinical research data. The DCC will monitor clinical sites to ensure compliance with data management requirements and Good Clinical Practices. The DCC is responsible for developing, testing, and managing clinical data management activities, as required, at the study sites, the CCC, and at the DCC.

The general NINDS Common Data Elements (CDE) will be used to construct data collection forms. All study data will be collected via systems created in collaboration with the DCC and will comply with all applicable guidelines regarding patient confidentiality and data integrity.

9.1.1 Enrollment Registration

Participants will be considered screened after signing the informed consent form for this study. Eligible screened participants will be 'randomized' once registered in the NeuroNEXT IWRS and considered 'dosed' only after receipt of study drug. Enrollment of participants on this protocol will employ an interactive data system in which the clinical study site will attest to the participant's eligibility as per protocol criteria after obtaining informed consent. NeuroNEXT CIRB approval for the protocol must be on file at the DCC before accrual can occur from the clinical study site. The participant is not considered validly enrolled until the first study infusion begins. If a participant becomes ineligible between randomization and the onset of study drug infusion, he/she will be considered a randomization failure and will be replaced.

The DCC will use a system of coded identifiers to protect participant confidentiality. When the participant is registered to participate in the study using the DCC-provided web-based registration, the system will assign a participant ID number. The unique ID code will include a protocol ID, a site ID, and a unique participant ID. To confirm the correct participant ID, the data entry system will require a second entry of the unique participant ID and compare for consistency. In this fashion, no personal identifiers would be accessible to the DCC and the data will be collected on the correctly identified subject.

9.1.2 Data Entry

Data entry will occur at the enrolling clinical study sites. Data quality assurance and analyses will be performed by the DCC. The DCC, located at The University of Iowa, will coordinate all data and statistical services for the study, as well as on-site monitoring for all participating clinical study sites.

Data collection for this study will be accomplished with online electronic case report forms. Using encrypted communication links, online forms will be developed that contain the requisite data fields.

9.2 Role of Data Management

Data Management (DM) is the development, execution and supervision of plans, policies, programs, and practices that control, protect, deliver, and enhance the value of data and information assets.

All data will be managed in compliance with NeuroNEXT policies, and applicable Sponsor and regulatory requirements. The DCC will instruct site personnel to collect, transcribe, correct, and transmit the data onto source documents, CRFs, and other forms used to report, track and record clinical research data. The DCC will monitor clinical sites to ensure compliance with data management requirements and Good Clinical Practices. The DCC is responsible for developing, testing, and managing clinical data management activities, as required, at the clinical study sites (CSS), the CCC, and at the DCC.

The DCC is responsible for all aspects of clinical data management, and for properly instructing key study personnel (including the CCC, the CSS, and DCC staff) on how to collect, transcribe, correct and transmit the data onto CRFs or other data collection forms and logs.

The DCC is responsible for establishing procedures to ensure that clinical data management activities occur as required at the CCC, the CSS, and at the DCC.

9.3 Quality Assurance

By signing this protocol, the Sponsor and Investigator agree to be responsible for implementing and maintaining quality control and quality assurance systems with written standard operating procedures (SOPs) to ensure that studies are conducted and data are generated, documented, and reported in compliance with the protocol, accepted standards of GCP, and all applicable federal, state, and local laws, rules and regulations relating to the conduct of the clinical study.

All participating clinical sites have been pre-qualified by the NeuroNEXT management team according to NeuroNEXT SOPs.

9.3.1 Development of Monitoring Plan

On-site monitoring visits will be conducted by DCC monitors according to a pre-defined Monitoring Plan. The Monitoring Plan will detail the frequency of on-site visits, the study data to be monitored, the review of any regulatory files, drug and supplies accountability (if applicable), documentation of the on-site visit, and the resolution process for data errors that are discovered during the visits. All participating clinical study sites will be monitored at least once after study initiation and all sites will have a close-out visit for each protocol. One on-site blinded monitoring visit is anticipated for each clinical study site per year. Additionally, one on-site unblinded pharmacy visit is anticipated for each site per year. All subjects will be monitored for inclusion and exclusion criteria, informed consent procedures, and adverse events. A certain percentage of data is also monitored/ source data verified against the data entered into the study database. The monitoring plan will include flexibility to revise the frequency of visits or data monitored depending on clinical study site or study related issues.

9.3.2 Site Monitoring Visits

On-site blinded monitoring visits will be conducted by DCC monitors according to a pre-defined Monitoring Plan for each protocol. The goal of on-site monitoring is to analyze (review) the data as it is collected, to check the validity and integrity of the data, to verify source documentation, to ensure protection of human subjects, and to ensure protocol compliance with federal regulations. During the monitoring visit, the monitor assesses the overall status of the study, staff, and facilities to determine whether the study is being conducted per protocol and in compliance with regulatory requirements. The monitor also conducts a CRF review that includes checks of all adverse event documentation, verifies the presence of all critical correspondence and records related to investigational products and clinical supplies (if applicable), and determines if protocol violations have occurred and are documented properly. After the monitoring visit, the monitor documents the results of the monitoring visit and completes a post-visit monitoring letter that conveys any issues discovered during the visit and the need for data corrections, if appropriate. Unblinded pharmacy monitoring visits will be conducted by independent monitors to ensure proper drug storage. handling and administration. Drug and supplies accountability may also be monitored during the site visit. The DCC will work closely with the unblinded pharmacy monitors to monitor and document drug distribution from the manufacturers to the clinical study sites (CSS). Each CSS will be provided with a drug accountability log, which will be reviewed by the independent monitors and reconciled with distribution logs. At the study closeout visit, the monitors confirm that appropriate data have been reviewed, source documentation has been verified, and all required documents are present in the Study Regulatory File.

9.3.3 Laboratory Data Flow

Safety Monitoring Labs: The DCC will provide clinical study sites with online forms and/or electronic data exchange mechanisms, depending on their capabilities and needs, in order to enter, update, and obtain relevant data. The CSS will be responsible for the entry of laboratory data into the electronic data capture (EDC) system.

9.4 Adverse Experience Reporting

The adverse event (AE) definitions and reporting procedures provided in this protocol comply with all applicable United States Food and Drug Administration (FDA) regulations and International Conference on Harmonization (ICH) guidelines. The Site Investigator will carefully monitor each subject throughout the study for possible adverse events. All AEs will be documented on CRFs designed specifically for this purpose. It is important to report all AEs, especially those that result in permanent discontinuation of the investigational product being studied, whether serious or non-serious.

AEs should be collected and reported on subjects who receive investigational treatment from signing of the ICF through study Day 7, and should be followed until resolution or a new baseline is established, but no longer than study Day 90. Any AEs that occur prior to informed consent should be included in the subject's medical history. SAEs will be collected and reported on subjects who receive investigational treatment from signing of the ICF through study Day 30, and should be followed until resolution (or resolution with sequelae), but no longer than study Day 90.

Each clinical study site's Principal Investigator and research team are responsible for identifying adverse events and reporting them through the DCC Online Adverse Event Reporting System. Investigators are also responsible for complying with NeuroNEXT CIRB's reporting requirements for all safety reports. Copies of each report and documentation of IRB notification and receipt will be kept in the Investigator's study file.

Headache has been identified as an AE that we would like to further characterize. Therefore, all headaches that start after signing of the ICF should be documented as AEs, and Investigators should also complete the Headache Record CRF. A new AE form and new Headache Record should be completed for each new headache during the first seven days. Headaches that start prior to signing of the ICF and do not worsen should be reported only on the Medical History CRF and the Headache Record CRF should not be completed. If however, a headache begins prior to consent and later worsens it should be reported as an AE and the Headache Record CRF should be completed.

On-line Adverse Event Reporting System

Upon entry of a serious adverse event by a site Investigator, the DCC Online Adverse Event Reporting System will immediately notify the Independent Medical Monitor (IMM).

 Within 24 hours (of learning of the event), Investigators must report any Serious Adverse Event (SAE). Investigators should report all other AEs within 5 working days/7 calendar days (of learning of the event).

Serious adverse events: The site Investigator determines causality (definitely not related, unlikely related, possibly related, probably related, definitely related) of the adverse event. The IMM will review the SAE report. The IMM may request further information if necessary. The Online Adverse Event Reporting System maintains audit trails and stores data (and data updated) and communication related to any adverse event in the study. The Sponsor in conjunction with the IMM may determine that the Serious Adverse Event requires expedited reporting to the FDA. The DCC will prepare a MedWatch safety report for submission to the FDA. If warranted, the IMM will notify

the DSMB chair. The DSMB may suggest changes to the protocol or consent form to the Study Chair as a consequence of adverse events.

Non-serious adverse events: Non-serious adverse events that are reported to or observed by the Investigator or a member of his/her research team should be submitted to the DCC in a timely fashion (within 5 working days/7 calendar days). See the 'Site Manual of Operations' for more detail. The events will be presented in tabular form and given to the IMM on a quarterly basis or as requested. Local site Investigators are also required to fulfill all reporting requirements of their local institutions.

The DCC will prepare aggregate reports of all adverse events (serious/not serious, expected/unexpected and relationship to study drug) for the IMM and the DSMB on a quarterly basis or as requested. In addition, all adverse events will be coded using the MedDRA system. A separate report detailing protocol compliance will also be available from the DCC for DSMB and/or site review monthly or as requested. The research team will then evaluate whether the protocol or informed consent document requires revision based on the reports.

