Dose-limiting toxicities will be assessed from the first dose to 48 hours following the last dose of study treatment (unless specified below) and defined as any of the following AEs that have an attribution of "related" to study treatment (possibly, probably, and definitely):

- An aPTT following any dose that reaches 2 x the ULN at 1 hour post-dose. Upper limit of normal range is defined locally by the site laboratory.
- SICH defined as blood present on CT or MRI brain images that is associated with clinical worsening that meets the definition of neuroworsening (4 or more point increase in NIHSS; see section 9.4.1.3 for definition) and in the opinion of the investigator represents a clinically significant change that can be attributed to the hemorrhage. Subarachnoid hemorrhage that occurs in subjects who receive mechanical thrombectomy will NOT be considered a DLT, and instead will be evaluated in an exploratory analysis upon study completion.
- Laboratory findings that meet all of the following three components (Hy's Law):
 - $\geq 3 \times ULN \text{ of ALT or AST},$
 - In combination with a serum total bilirubin (TBL) >2 x ULN, without initial findings of cholestasis (serum ALP activity >2 x ULN),
 - And, no other reason can be found to explain the combination of increased aminotransferase (AT) enzymes and TBL, such as viral hepatitis A, B, or C, preexisting or acute liver disease, or another drug capable of causing the observed injury.
- Any other bleeding event classified as serious by the Investigator, or any bleeding that required the administration of more than 2 units of packed red cells over any two consecutive days.

- Any Grade 3 laboratory value that, in the opinion of the Investigator, is related to study treatment. Refer to CTCAE v4.03 sections relevant to laboratory investigations.
- Any adverse event that, in the opinion of the Investigator, is related to study treatment and leads to cessation of further dosing.

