The monitoring of subject safety and data quality will follow the NINDS Guidelines for Data and Safety Monitoring in Clinical Trials. A Data and Safety Monitoring Board (DSMB) appointed by the NIH/NINDS will meet at approximately six-month intervals (or as determined by the NINDS) to review partially unblinded study data provided by the study statistician. This committee will monitor rates of adverse events and endpoints in the trial and will monitor the performance of the trial. The frequency and format of DSMB meetings, reports, and guidelines for interim analysis will be agreed upon prior to study subject enrollment. The PPI will appoint an IMM to review all adverse events, in a blinded fashion. The IMM will perform a review of Day 1-7 data (including non-serious AEs) on Day 8 to look for missed DLTs. During that same Day 8 review the IMM will evaluate for safety and for neuroworsening all AEs that have been reported. Any non-serious AEs that occur during the DLT period but are not reported until after the Day 8 review will be evaluated in real time by the

IMM for safety, neuroworsening, and DLTs. Any non-serious AEs that occur after the DLT observation period can be reviewed on a quarterly basis or sooner at the discretion of the IMM. In addition the IMM will review all events that meet the regulatory definition of a Serious Adverse Event (SAE), upon receipt of notification via the Electronic Data Capture (EDC) system, for safety, neuroworsening and DLTs. See the Safety Management Plan for more detail.

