6 STUDY PROCEDURES

6.1 Schedule of Activities

Procedure	Screen/ Pre- Dose 1	Study Day 1⁵	Study Day 2⁵	Study Day 3⁵	Study Day 4 ⁶	Study Days 5- 6 ⁶	Study Day 7, or Discharge +/-3 days	Study Day 14 +/-4 days	Study Day 30 +/-5 days	Study Day 90 +/-10 days
tPA Administration or Mechanical Thrombectomy ¹	SOC									
Informed Consent ²	Х									
Inclusion/Exclusion	Х									
Medical History	SOC									
Weight ³	Х		X ³							
Acute Blood Pressure Monitoring ⁴	SOC	SOC								
Vital Signs ⁷	SOC	Х	Х	Х	SOC	SOC	Х		Х	Х
Physical Exam	SOC		SOC	SOC	SOC	SOC	Х		Х	Х
Neurologic Exam: NIHSS ⁸	Х		Х	Х	Х	Х	Х		Х	Х
Modified Rankin Scale	Х								Х	Х
Barthel Index									Х	Х
Brain Imaging (CT or MRI)9	SOC		SOC							
Brain Imaging (MRI) ¹⁰							Х		Х	Х
Serum Chemistry ¹¹	SOC / X		Х	Х	Х					
CBC ¹²	SOC		Х	Х	Х					

Procedure	Screen/ Pre- Dose 1	Study Day 1⁵	Study Day 2⁵	Study Day 3⁵	Study Day 4 ⁶	Study Days 5- 6 ⁶	Study Day 7, or Discharge +/-3 days	Study Day 14 +/-4 days	Study Day 30 +/-5 days	Study Day 90 +/-10 days
Coagulation Studies ¹³	SOC	Х	Х	Х						
Urinalysis – Dipstick ¹⁴	Х		Х	Х	Х					
Pregnancy Test ¹⁵	Х									
ECG	SOC		X ¹⁶	1						
3KA-APC Plasma Antibody	Х							Х	Х	
Blood for PK			X ¹⁷							
Study Drug Administration ¹⁸		Х	Х	Х						
AE Assessment		x	х	x	x	x	X ²⁰		X ^{19,20} SAEs only	
Con Med Assessment		Х	Х	Х	Х	Х	X ²⁰		X ^{19,20}	
DLT Assessment Confirmation							Х			
Discharge Medications							Х			

¹ **tPA or Mechanical Thrombectomy:** Subjects will be eligible to consent for this study following initiation of tPA administration or the decision to begin mechanical thrombectomy, whichever occurs sooner.

² Informed consent: Informed consent (and re-consent, as applicable) must be obtained by the CSS PI or a qualified designee (licensed physician investigator) listed on the FDA Form 1572. If informed consent was originally provided by a legally authorized representative, and, in the opinion of the CSS PI, the subject's mental status improves sufficiently to enable him/her to provide informed consent, the subject must be re-consented in person at the current or next study visit. Re-consenting once the subject regains capacity is an expected part of Good Clinical Practice (GCP).

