8.4 Data Monitoring

All aspects of the study will be monitored by qualified individuals designated by the sponsor. Monitoring will be conducted according to Good Clinical Practice and applicable government regulations. The Investigator agrees to provide monitors access to the clinical supplies, dispensing and storage areas, and to the clinical files of the study subjects, and, if requested, agrees to assist the monitors. The site will provide the monitor adequate working space and full access to the medical record. If the site uses an electronic medical record, the monitor will be provided a temporary password and access to one patient chart, or, the site coordinator will be available throughout the monitoring visit to provide access. The site PI will be available for an exit visit with the monitor.

Safety monitoring will include careful assessment and appropriate reporting of adverse events. Medical monitoring will include contemporaneous assessment of serious adverse events.

The monitoring of subject safety and data quality will follow the NINDS Guidelines for Data and Safety Monitoring in Clinical Trials. A Data and Safety Monitoring Board (DSMB) appointed by the NIH/NINDS will meet at approximately six-month intervals (or as determined by the NINDS) to review partially unblinded study data provided by the study statistician. This committee will monitor rates of adverse events and endpoints in the trial and will monitor the performance of the trial. The frequency and format of DSMB meetings, reports, and guidelines for interim analysis will be agreed upon prior to study subject enrollment during the first meeting of the DSMB with the representatives of the DCC. The DSMB will review the data seen by the SRC during their deliberations of dose escalation steps.

The Protocol PI will appoint an Independent Medical Monitor (IMM) to review all adverse events in a blinded real-time fashion in order to monitor for AEs that could meet the definition of a DLT. Should a DLT be reported or suspected, the IMM will notify the SRC, which will be convened to review the AE(s). In addition, the IMM will review all events that meet the regulatory definition of a Serious Adverse Event, upon receipt of notification via the Electronic Data Capture (EDC).

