- 3. Possibly Related: The reaction follows a reasonably temporal sequence from administration of the investigational product and follows a known response pattern to the suspected investigational product; the reaction could have been produced by the investigational product or could have been produced by the subject's clinical state or by other modes of therapy administered to the subject. (suspected ADR)
- 4. Probably Related: The reaction follows a reasonably temporal sequence from administration of investigational product; is confirmed by discontinuation of the investigational product or by rechallenge; and cannot be reasonably explained by the known characteristics of the subject's clinical state. (suspected ADR)
- 5. Definitely Related: The reaction follows a reasonable temporal sequence from administration of investigational product; that follows a known or expected response pattern to the investigational product; and that is confirmed by improvement on stopping or reducing the

dosage of the investigational product, and reappearance of the reaction on repeated exposure (suspected ADR).

Recording of Adverse Events

All clinical adverse events are recorded in the Adverse Event (AE) data entry template in the subject's study binder. The site should fill out the AE data entry template and enter the AE information into the online Adverse Event Reporting System within 5 working days/7 calendar days of the site learning of a new AE or receiving an update on an existing AE.

Please Note: Serious Adverse Events (SAEs) must be reported to the NeuroNEXT Data Coordinating Center within 24 hours of the site learning of the SAE.

Entries in the AE data entry template (and into the online Adverse Event Reporting System) will include the following: name and severity of the event, the date of onset, the date of resolution, relationship to investigational product, action taken, and primary outcome of event.

Adverse Events and Serious Adverse Events - Reportable Events

The following are considered reportable events and must be reported to the NeuroNEXT Data Coordinating Center within 24 hours of the site being notified of the event.

• All events that meet the above criteria for Serious Adverse Events (SAEs)

All occurrences of Serious Adverse Events (SAEs) must be reported within 24 hours of discovery of the event. All other Adverse Events (AEs) should be reported *within 5 working days*/7 *calendar days (of discovery of the event).*

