10.6 Safety Review Committee

An independent Safety Review Committee (SRC) will be formed and charged with reviewing and adjudicating DLTs in order to objectively inform the CRM. The SRC will be comprised of a committee chair, the IMM, and three qualified participants – as outlined in the 'Safety Review Committee Charter'. For every reported DLT, the SRC will review the event and make a final determination as to whether or not an incident should be classified as a DLT. The SRC's final adjudication (DLT = yes/no) will be recorded using the DLT Adjudication Form as part of the IMM Evaluation Module. Assignment of the dose for the following cohort will not occur until all four subjects in a cohort have completed the Day 8 assessment and all potential DLTs have been reviewed by the SRC. The SRC will be responsible for final determination of whether a particular AE will be classified as a DLT, but will not participate directly in dose selection. On a quarterly basis, the SRC will also review the same aggregate reports viewed by the IMM (see section 10.5).

If in the extraordinarily unlikely event the Central Reader identifies a new suspected DLT that was not previously recognized for that subject, the Central Reader will inform the PPI who will contact the DCC to initiate the AE/DLT review process so that the DLT can be adjudicated by the SRC.

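### A non-serious DLT may be reported on time yet after the Day 8 review, because only SAEs carry a 24-hour limit, so an interim dose can be assigned on an incomplete DLT count

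*Protocol*

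**What the plan says.** **Reporting limits.** Protocol 9.4.1.5 states: "All occurrences of Serious Adverse Events (SAEs) must be reported within 24 hours of discovery of the event". Its list of 24-hour reportable events has that one entry. For non-serious events, Protocol 9.4 says that they "should be submitted to the DCC in a timely fashion (within 5 working days/7 calendar days". Protocol 9.4.1.5 and SAP 10.1 repeat the longer limit. Neither document sets a separate limit for a DLT.

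**DLT criteria.** Protocol 3.1.1 and 8.2.1 and SAP 2 include events that need not be serious. One is "Any Grade 3 laboratory value that, in the opinion of the Investigator, is related to study treatment"; others are an aPTT at twice the ULN and a related event that ends dosing. By contrast, the cause of neuroworsening is always recorded as an SAE (Protocol 9.4.1.3), so SICH falls under the 24-hour rule, as does any bleed classified as serious.

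**Review and release.** Protocol 3.1.3: "The IMM will perform a review of Day 1-7 data (including non-serious AEs) on Day 8 to look for missed DLTs". Under SAP 10.6 the next cohort's dose is not assigned "until all four subjects in a cohort have completed the Day 8 assessment and all potential DLTs have been reviewed by the SRC". SAP 7 adds that the statisticians are alerted once the cohort's DLT status is complete. The site's own "DLT Assessment Confirmation" is marked in Protocol 6.1 at the Day 7 or discharge visit, with a window of 3 days either side.

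**Late reports.** Protocol 3.1.3 and SAP 10.5 foresee DLT-period events that arrive after the Day 8 review. The IMM is to evaluate them in real time. Neither text says what then happens to a dose already assigned.

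**The concern.** The DLT count is the primary endpoint and the only input to the dose model. If the reporting limit for some DLT types runs past the review that completes a subject's DLT status, a site can keep every rule while the model treats a subject with a DLT as having none. Subjects could then be assigned a dose on that count before the report arrives. The SRC does not remove the problem, because it can adjudicate only events already reported or suspected.

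**Working it through.** The plan states no figure on this point, so there is none to reproduce. The check is calendar arithmetic, followed by two illustrations on stated assumptions.

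**1. End of the DLT window.** Five doses 12 h apart (Protocol 5.4), plus 48 h (Protocol 3.1.1): 4 × 12 + 48 = 96 h after dose 1, which is Day 5. With every interval at 11 h or 13 h, the total is 92 h or 100 h. Depending on the clock time of dose 1, the window then ends between Day 4 and Day 6.

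**2. Latest on-time report.** Deadline = day learned + 7 calendar days.

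| Learned | Non-serious limit | 24-hour limit |
|---|---|---|
| Day 1 | Day 8 | Day 2 |
| Day 2 | Day 9 | Day 3 |
| Day 3 | Day 10 | Day 4 |
| Day 4 | Day 11 | Day 5 |
| Day 5 | Day 12 | Day 6 |

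From Day 2 onward the present limit falls after Day 8, by 1 to 4 days for events learned on Days 2 to 5. An event first learned on Day 7 is on time until Day 14.

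**3. Site confirmation.** Day 7 ± 3 runs from Day 4 to Day 10. It can precede the end of the DLT window or follow the Day 8 review.

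**4. The version 8.0 lag.** Once cohort n is enrolled, cohorts 1 to n-1 set the dose for cohort n+1 (Protocol 8.1.1). A late DLT in cohort n-1 then misses that assignment only if cohort n fills first. Planned accrual is 0.3 × 15 = 4.5 subjects a month (Synopsis), so a cohort takes about 4/4.5 × 30.4 = 27 days. With Poisson arrivals, P(at least 4) = 1 - e^(-λ)(1 + λ + λ²/2 + λ³/6):

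- 12 days: λ = 4.5/30.4 × 12 = 1.78, giving 10%
- 14 days: λ = 2.07, giving 16%
- at twice the accrual rate: 47% and 59%

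This assumes that the model is run when cohort n fills. If it is run as soon as cohort n-1's DLT status is complete, as SAP 7 suggests, the lag protects only if someone reruns it, and no rerun is specified.

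**5. Effect of one missing DLT (illustration).** The model is p = s^a, with s = 5, 7, 9 and 11% and the posterior mean of a plugged in (SAP 7). The documents give no prior for a. I assumed four: Exp(1), and lognormal with median 1 and log-sd 0.5, 1.0 or 1.34. The allocations are also assumed.

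| Treated so far | DLT missing | DLT included |
|---|---|---|
| 3 at 120 | 0/3: a = 1.25 to 3.43; every dose at 6.4% or less; one-level escalation | 1/3: a = 0.49 to 0.73; 120 at 11.3-23.0%; no dose within 10% |
| 3 each at 120, 240, 360; DLT at 360 | 0/9: 540 at 4.0% or less; model dose 540 | 1/9: a = 0.92 to 0.96; 540 at 12-13%; model dose 240 (360 with log-sd 0.5, where 0.09^0.958 = 9.95%) |
| 33 (3/3/6/21), DLTs at 540 | 2 DLTs: 540 at 6.3-7.0%; model dose 540 | 3 DLTs: 540 at 9.5-9.7%; model dose still 540 |
| Same 33 | 3 DLTs: model dose 540 | 4 DLTs: a = 0.94 to 0.95; 540 above 12%, 360 just above 10%; model dose 240 |

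The missing event matters with few subjects treated, or when an estimate is already close to 10%.

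**The case against.** The strongest reply is that several layers stand between a slow AE form and a wrong dose.

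- **The lag.** It usually leaves time for the report, as step 4 shows. This stands as a reduction, not a cure, and it weakens if accrual is fast.
- **All four subjects must clear Day 8.** At planned accrual, reports on a cohort's earlier subjects will normally be in. This stands: the exposure is mainly to the last subjects treated.
- **The Day 8 profile.** SAP 10.5 puts laboratory results, infusions and site-reported DLTs before the IMM, so all three non-serious types named here may be seen without an AE form. This stands in part: the documents supplied give no deadline for entering those data.
- **Early Day 7 visits.** A documented phone call must capture AEs through actual Day 7 (Protocol 6.1, note 20). That answers much of the worry about discharge, but an event captured that way keeps its 7-day reporting limit.
- **Other manuals.** Protocol 9.4 points to the Site Manual of Operations, and the Safety Management Plan and SRC Charter are also cited. Any of them may hold a DLT-specific limit. None was supplied, so its absence cannot be asserted.

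A reader might infer a flat contradiction on IMM access. Protocol 8.4 has the IMM "review all adverse events in a blinded real-time fashion in order to monitor for AEs that could meet the definition of a DLT", while Protocol 9.4 gives quarterly tables of non-serious events and 9.4.1.5 gives monthly ones. Protocol 3.1.3 and SAP 10.5 largely settle this: DLT-period events are reviewed on Day 8, or in real time if late, and later events quarterly. Only the quarterly and monthly wording remains to be aligned.

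**Conclusion.** The gap is real but bounded. Under the limits in both documents, a non-serious DLT learned on Day 2 or later can be reported on time after the Day 8 review, and the handling of an assignment already made is not stated. What is exposed is an interim dose assignment, mainly through the last subjects of a cohort.

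Two stronger inferences are not supported. One is that the MTD would rest on a count that omits late DLTs: SAP 7 runs the final model on all observed data, so a late DLT enters later runs and the MTD. The other is that the swing after three treated subjects is typical. Direct release of cohort 2 from cohort 1 belongs to the process used through version 7.1, and with 33 treated subjects in the allocation above, 2 versus 3 DLTs gives the same dose.

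The calendar result needs only the stated limits. The 10-16% assumes Poisson arrivals at planned accrual and a model run when the next cohort fills. The dose effects depend on assumed priors and allocations. The conclusion also depends on whether the manuals not supplied already set a DLT limit.

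**What to change.** 1. Add to the 24-hour reportable list any event that meets, or is suspected of meeting, a DLT criterion, serious or not (Protocol 9.4 and 9.4.1.5; SAP 10.1). Events learned on Days 2 to 6 would then be due by Days 3 to 7.
2. Before the IMM closes a subject, require the site's DLT confirmation, dated after the 48-hour window has ended, and entry of all laboratory results from within the window.
3. State that a DLT reported after closure triggers a model rerun before further subjects are assigned on the count that lacks it.
4. Reconcile this with the Site Manual of Operations, Safety Management Plan and SRC Charter, and align the quarterly and monthly wording for the IMM's tables of non-serious events.

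The cost is 24-hour entry for a few events, one closing condition in the data system, and an occasional short delay in closing a cohort. When two cohorts are full, that delay could send an additional subject to placebo, which the lag was meant to limit.
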